Patients ≥ 65 years will be recruited from the UAB and BVAMC cardiology, advanced HF, geriatric, and primary care clinics and from [name] (co-I)^{160,163} existing UAB HF study cohorts. HF occurs most commonly in older adults and the Seattle Heart Failure model¹⁶⁷ has demonstrated some ability to identify patients who might benefit from palliative care.⁴¹ These broad criteria, consistent with a pragmatic design, balance the competing issues of sample homogeneity and external validity/generalizability.

Patient Inclusion Criteria: 1) English-speaking; 2) able to complete baseline interview (see Instruments-Appendix E); 3) Age ≥ 65 ; 4) NYHF III/IV or ACC Class D HF (physician-determined); 5) Seattle Heart Failure Model $\geq 50\%$ 2 year mortality (<http://depts.washington.edu/shfm/>)^{41,167}

Patient Exclusion Criteria: 1) Dementia or significant confusion (measured by ≤ 3 Callahan score¹⁶⁸ 2) DSM-IV Axis I diagnosis (e.g. schizophrenia, bipolar disorder, or active substance use disorder); 3) Patients will not be excluded if they do not identify a caregiver.*

* We have consciously chosen to make allowances (in this and our prior intervention studies) in favor of a pragmatic approach recognizing that many chronically-ill patients have little or no caregiver support. We recognize that caregiver support can positively influence some HF outcomes and if imbalance.^{39,110,169}

Specific Aim 2 Caregiver Sample and Justification

Consistent with our prior studies^{50,51,63 102} and a pragmatic design we will use a broad definition of "caregiver".

Caregiver Inclusion Criteria: 1) Identified by the patient as "a person who knows you well & is involved in your medical care". May live in the same household and/or be considered to be primary caregiver willing to participate;¹⁰² 2) English-speaking; 3) able to complete baseline interview (see Instruments-Appendix E)

C2.3 Total Enrollment

We anticipate a total enrollment of 380 patient participants and 228 caregivers over 42 months (from our previous studies, ~60% caregivers participated). Approximately half of the patient participants (n=190) will be randomized to the intervention and half (n=190) will be randomized to receive usual HF care. Likewise, due to stratified randomization by indication of caregiver, approximately half of caregivers (n=114) will be randomly assigned to intervention and the other half to usual care (control) (n=114).

Justification of Enrollment Estimates

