Participant receipt / enactment of intervention: Following the collection of outcome measures at week 48, all intervention participants will be interviewed by phone for the primary purpose of determining if the patient received and enacted the components of the intervention as described in Table 2. We will use procedures and interview guides that have been adapted from our previous RCTs.⁶⁷ Briefly we will digitally-record, transcribe all interviews verbatim, and code transcripts using ATLAS.ti software to determine the extent of patient receipt and enactment of the skills taught by the nurse coaches. The PI is an experienced qualitative researcher,¹⁷⁰⁻¹⁷⁴ with expertise in the qualitative techniques that are recommended for intervention evaluation.^{175,176} Though not the purpose in this proposal, these interviews may also provide rich data for a secondary analysis of the patient and caregiver experience.

C4 INSTRUMENTS (All instruments are contained in Appendix E.)

The instruments were carefully chosen to measure distinct constructs within the theoretical models (Figures 1a and 1b) with little to no overlap. The proposed instrument battery and schedule are similar to what we have used in our prior studies^{50,51,177} and in our recent HF pilot study.⁶⁸ Per pilot participants' report⁶⁸ these presented minimal burden.

Table 3. Outcome measures

Specific Aim 1					
	Construct	Instrument	Description	Reliability	Schedule
HF Patients	QOL	Kansas City Cardiomyopathy Questionnaire (KCCQ) ¹⁷⁸	5 domains: physical limitations, symptoms, self-efficacy, social interference, and QOL; 23 items	Subscales α =.62 to .90	Baseline, week 8 and every 8 weeks until week 48
	Mood	Hospital Anxiety and Depression Scale (HADS) ¹⁷⁹	2 domains measuring depression and anxiety; 14 items	Subscales α =.82 to .83	
	Symptom Burden	Memorial Symptom Assessment Scale-HF (MSAS-HF) ²⁵	Targets 32 HF-relevant symptoms (e.g. chest pain, difficulty breathing while lying flat, etc.)	Subscales α =.73 to .92	
	Resource use	Resource Use	Inpatient days, ICU days, ED visits, hospice use, palliative care provider visits, AD completion, DNR orders	NA	
Specific Aim 2					
Caregivers*	QOL	Quality of Life – Caregiver (QOLC) ¹⁸⁰	3 domains: emotional and spiritual well-being; relationship with patient; & sleep, daily routine, and family life, 35 items	α = 0.91	Baseline, week 8 and every 8 weeks until week 48
	Mood	Hospital Anxiety and Depression Scale (HADS)	Same as above	Same as above	

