Data Security: All databases are secure, HIPAA-compliant and password protected in both the front end and back end. Back end data will be housed on a secure drive with access limited to only authorized research personnel.

C5 STATISTICAL CONSIDERATIONS

C5.1 Randomization. After consent and baseline assessment, patients will be randomized using computer-generated treatment assignments, stratified by center (UAB or BVAMC), referring service (HF clinic, cardiology, primary care), and race (Caucasian/non-Caucasian).

C5.2 Statistical Analyses

Specific Aim 1 Patient-reported QOL, mood, symptom burden, and resource use

The intention to treat (ITT) analysis will be used for all treatment comparisons. That is, all randomized patients will be included in primary comparisons, regardless of whether the patient actually received the randomly-assigned intervention. Primary data analysis will begin with descriptive statistics for baseline patient characteristics and outcomes by treatment group. Distributional assumptions will be examined; when appropriate we will employ testing and modeling procedures that do not assume normality. We will compare groups with respect to baseline covariates. We will analyze and compare missing data and compliance patterns according to baseline covariates and we will adjust analyses for baseline factors showing either imbalances or predictive of missing data (not due to patient death) or compliance. Mixed modeling techniques and covariate adjustment will reduce the impact of missing data, provided that the data are missing at random. If necessary, multiple imputation techniques and sensitivity analyses will be used to deal with data not missing at random and not caused by patient death.

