We will conduct 2 sets of longitudinal ITT analyses of the primary study endpoints for participants with baseline and one or more follow up assessments using mixed effects modeling for repeated measures to examine the relative impact of ENABLE: CHF-PC in the 48 weeks after enrollment (forward in time from baseline), and its effects proximal to the time to death (retrospective starting from death). In the first set of analyses, we will examine differences between all patients in each group surviving until the scheduled 48 week follow-up surveys. Kurland et al.¹⁴⁷ have described this approach as a partially conditional analysis for joint longitudinal and survival data, because it assumes that patients are alive at the comparison times.¹⁴⁷ Initial ITT analyses will be conducted on patient-reported outcomes using mixed effects models to test the effect of the intervention, first by comparing all group differences simultaneously for both time periods in multiple degree of freedom global tests, and then individually if overall differences are significant.

The second analysis, retrospective from death, also conducted with mixed effects models, has been described by Kurland et al.¹⁴⁷ as fully conditional; because it examines patient outcomes conditional on the patients having died (the participants who are alive by the end of follow-up are excluded because their outcome measures proximal to death will be unknown). Alternative more complex analyses involving “terminal decline” models that jointly model a longitudinal outcome and survival will be considered as described under Exploratory Aim 2 below. All calculations will be performed using the latest versions of SAS and R. Standardized intervention effect sizes will be estimated for each outcome, and the False Discovery Rate criterion will be used to correct for multiple significance testing. We will conduct a decedent-only ITT analysis for the proxy-report QODD. Since only one QODD observation will be available for each decedent, no longitudinal modeling is required. Secondary analyses will consider any deviations from the intended intervention, and intervention dose effects. Subgroup analyses will be conducted with interest on

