determining the profile characteristics (e.g. race, SES, gender, military vs. civilian background, absence of caregiver, etc.) of the participants who benefited the most and the least from the intervention using flexible modeling techniques, such as latent class analysis and recursive partitioning.

Specific Aim 2 Caregiver QOL, mood, self-reported health, burden

Caregiver outcomes will be analyzed using the same longitudinal methods as outlined for Specific Aim 1. For the analyses going forward in time from baseline, the effects of patient death on caregiver outcomes will be examined using models with indicators for patient death at its respective time-point. Only decedents' caregivers will have grief outcomes analyzed which will not involve longitudinal modeling. Caregivers of patients who die will contribute the additional outcome of a rating of quality of care at the end of life (QODD). Since only one QODD observation will be available for each decedent, no longitudinal modeling is required. However, analysis of these measures will be conducted with mixed effect methods to account for nesting, with the parameter of interest being the association between group assignment and the caregiver-rated outcome

Exploratory Aim 1. Explore mediators/moderators of patient/caregiver outcomes and reciprocal relationships.

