228 caregivers. We assume an exponential survival distribution with a median of 2 years and independent 2-year 10% attrition. Under these assumptions, we estimate the minimum detectable difference (MDD) between the intervention and control patient means at every 8 weeks post randomization for 48 weeks as described in Table 4. We apply this same method to caregivers (Table 5) who will have their follow-ups truncated at patient death. We use ENABLE II data to provide estimates for the caregiver MBCB-OB standard deviation (sd).¹²⁹ Based on the meta-analysis by Garin et al.¹⁹² Literature-based estimates are used for the KCCQ,¹⁹³ HADS,^{179,194} MSAS-HF,²⁵ and QOL-C.¹⁰⁴ Patient and caregiver MDDs shown in Table 4 and 5 are based on partially-conditional (on being alive) time-averaged tests of mean differences comparing the treatment groups at the specified follow-up times, intra-subject correlation of 0.5, with a corrected two-sided .01 significance level, and a power of 0.80. Under these conservative assumptions we have sufficient sample size for the primary aims of this study. For subgroup analyses (e.g. Caucasian race vs. other) the detectable time-averaged standardized difference in intervention effect by 48 weeks post randomization is 0.53, assuming equally sized subgroups, and prior to other covariate adjustment.

It is estimated that 120 patients (60 per group) will die by 48 weeks post-randomization and will be available for the analysis of patient outcomes nearest death. Based on the sds in Table 4, we find MDDs of 10.8 for KCCQ, 1.04 for MSAS-HF, 2.06 for HADS-A, and 2.01 for HADS-D. We project that the grief index (ICG) will be available for 37 caregivers in each group. With a sd of 11.7,⁶³ a 5% two-sided significance level and 80% power, the MDD of the ICG between two groups is 7.7 using a two-sample t-test.

For secondary comparison of survival outcomes, we make the same assumptions about median survival, attrition, accrual, and observation time as for the longitudinal outcomes. Based on a log rank test, .05 significance level and a power of .80, a 1-yr reference survival fraction of 0.68, the detectable HR is 1.6.

C6 Potential problems, alternative strategies, and benchmarks for success and future directions.

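### The forward-in-time mixed models give the outcome's own baseline score and the randomisation strata no fixed place; the only covariate rule picks terms from the trial data

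*Combined protocol and SAP*

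**What the plan says.** Section C5.2, Specific Aim 1, says of baseline covariates: "we will adjust analyses for baseline factors showing either imbalances or predictive of missing data (not due to patient death) or compliance". It gives no threshold and no list of candidate factors. The next sentence explains the purpose: "Mixed modeling techniques and covariate adjustment will reduce the impact of missing data, provided that the data are missing at random".

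The longitudinal models are mixed-effects models for repeated measures, run "for participants with baseline and one or more follow up assessments". Baseline appears there as a condition for entry and as the time origin, and nothing is said about where it stands in the model. Under Specific Aim 2: "Caregiver outcomes will be analyzed using the same longitudinal methods as outlined for Specific Aim 1". The one term added there is an indicator of patient death, which is post-baseline.

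C5.1 describes randomisation as "stratified by center (UAB or BVAMC), referring service (HF clinic, cardiology, primary care), and race (Caucasian/non-Caucasian". No analysis section enters these factors in the forward models; race returns only for subgroups. C2.3 Total Enrollment expects equal caregiver numbers "due to stratified randomization by indication of caregiver", a factor that C5.1 does not list.

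Table 3 schedules the patient- and caregiver-reported outcome scores at "Baseline, week 8 and every 8 weeks until week 48". C5.3 says the detectable differences in Tables 4 and 5 rest on "time-averaged tests of mean differences comparing the treatment groups at the specified follow-up times, intra-subject correlation of 0.5", with a corrected two-sided .01 level and power .80.

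**The concern.** A baseline covariate gains precision through its correlation with the outcome. Chance imbalance between arms is a poor guide to that. The outcome's own baseline score is usually among its strongest predictors, yet under this rule it enters only if it happens to be imbalanced or to predict missingness or compliance. The strata were important enough to balance by design but have no stated place in the model.

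The text also allows several models: baseline as a covariate, as a response constrained to be equal between arms, as an unconstrained response, or only as an entry condition. These differ in precision, and the choice could be made after the data are seen. Tables 4 and 5 then do not describe any one defined analysis.

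**Working it through.** **Inputs.** From C5.3 and Table 4: KCCQ SD 21; alpha .01 two-sided and power .80, so z-sum 2.576 + 0.842 = 3.418; intra-subject correlation rho = .5; N = 356, 334, 313, 294, 276, 259 at weeks 8 to 48. Equal allocation. Let r be the correlation of baseline with each follow-up. The plan gives no separate value, so I use r = .5 (equal to rho) and r = .3 (assumption).

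**Formula at fixed n.** MDD = 3.418 × SD × sqrt(4v/n), with m averaged measurements:

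- follow-ups only: v = (1 + (m−1)rho)/m
- baseline-adjusted: the same v minus r²
- change from baseline: the same v plus 1 − 2r

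**Step 1: reproduce Table 4 (KCCQ).**

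| Week | Stated | Baseline as one more averaged measurement | Follow-ups only | Power of follow-ups only at stated value |
|---|---|---|---|---|
| 8 | 6.60 | 6.59 | 7.61 | .65 |
| 16 | 6.41 | 6.41 | 6.80 | .74 |
| 24 | 6.41 | 6.41 | 6.62 | .77 |
| 32 | 6.49 | 6.48 | 6.62 | .78 |
| 40 | 6.60 | 6.60 | 6.69 | .79 |
| 48 | 6.72 | 6.74 | 6.81 | .79 |

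The table reproduces within 0.02 only when baseline is counted among the averaged measurements (m = 2 to 7). That does not match the C5.3 description of tests at the follow-up times. Baseline-adjusted values match at week 8 alone (6.59) and reach 5.15 at week 48. Table 5 shows the same pattern: follow-ups only gives .467 against .405 at week 8 (power .65) and .419 against .414 at week 48 (.79). So the tables do not settle how baseline enters.

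**Step 2: fixed n at week 48** (n = 259, m = 6). Here v = 3.5/6 = .583 and 3.418 × 21 × sqrt(4/259) = 8.92.

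- follow-ups only: 8.92 × sqrt(.583) = 6.81
- adjusted, r = .5: 8.92 × sqrt(.333) = 5.15
- adjusted, r = .3: 8.92 × sqrt(.493) = 6.26
- change from baseline: 6.81 (r = .5), 8.84 (r = .3)

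**Step 3: all available visits.** Generalised least squares, with the Table 4 numbers taken as monotone dropout, free visit means, one constant arm effect and compound symmetry at .5 (assumptions on dropout and constant effect).

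| Role of baseline | KCCQ MDD, r = .5 | r = .3 |
|---|---|---|
| Not used | 5.96 | 5.96 |
| Covariate or constrained response | 4.56 | 5.50 |
| Unconstrained response, follow-up contrast | 5.94 | 5.96 |
| Unconstrained response, change from baseline | 5.94 | 7.66 |

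The variance ratios for adjusted against not used are .585 and .851. The first gives 1/.585 = 1.71, or 71% more patients; the second gives 1/.851 = 1.18, or 18% more. If rho and r both move to .3 or .7 (assumption), the ratio of MDDs is .89 or .60. For caregivers (Table 5 numbers, SD units), the MDD is .366 unadjusted, .280 adjusted at r = .5 and .338 at r = .3.

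**Step 4: size of the test under an imbalance rule.** Suppose baseline enters only if its arm difference has p below a cut-off of .05 to .20 (assumption). The correlation between the baseline and follow-up arm differences is r/sqrt(7/12). A bivariate normal integral for the unselected part, plus cut-off × .01 for the selected part, gives a true size for the nominal .01 test of .0059 to .0042 at r = .5 and .0086 to .0076 at r = .3. The rule is conservative. By the imbalance route alone, a .05 cut-off admits baseline in about 5% of trials.

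**Step 5: strata.** The documents give no variance share. If the strata explain 2% to 10% of the variance left after baseline (assumption), the MDD falls by 1 − sqrt(1 − R²), or 1% to 5%.

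**The case against.** The strongest reply is that this is lost efficiency and not an error. Comparing follow-up scores between randomised arms is valid, the selection rule makes the test conservative, and follow-ups alone at week 48 detect 6.81 against the stated 6.72 (power .79). All of that stands; the trial is not shown to be too small.

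Second, the plan may already intend baseline as a response: the models run forward from baseline, and Table 4 counts it. If that response is constrained, nothing is gained; the same holds if the rule selects baseline, and the chance of selection through missingness or compliance was not estimated. This limits the size of the benefit but leaves the gap, because the text never says constrained or unconstrained and the unconstrained version gains almost nothing for the follow-up contrast.

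Third, the 23% reduction needs r = .5; at .3 it is 8%. That stands.

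Fourth, C5.2 begins with global tests on several degrees of freedom, while the figures above are for one. For a 6-df test over six visits with a constant effect (assumption), the MDDs become 7.58 unadjusted, 5.80 adjusted at r = .5 and 6.99 at r = .3. The absolute values change; the ratios do not.

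Finally, two nearby texts mention model terms: the patient-death indicator for caregivers, and a remark in C5.3 that the subgroup figure precedes further covariate adjustment. The first is post-baseline and the second names no covariate, so neither fills the gap.

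**Conclusion.** The concern holds. The only baseline-covariate rule for the forward models selects terms from the trial data, and neither the outcome's baseline score nor the strata have a stated place.

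Fixed adjustment for baseline lowers the detectable KCCQ difference by about 8% to 23% (r = .3 to .5) relative to a model that does not use baseline. This assumes compound symmetry, monotone dropout at the Table 4 numbers and a constant effect, and that baseline is neither already a constrained response nor selected by the rule. The gain from the strata is smaller and wholly assumed. Confidence is high on the omission and lower on the size of the benefit. The change should be made, but its absence does not invalidate the trial.

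**What to change.** - In each forward-in-time model of a patient- or caregiver-reported score measured at baseline (KCCQ, HADS, MSAS-HF, QOLC, MBCB, PROMIS), include as fixed terms the baseline value of that outcome, stated as a covariate or a constrained baseline response, and centre, referring service and race as main effects.
- Drop imbalance as a selection criterion. Keep baseline predictors of missingness as additional terms, chosen from a candidate list named in advance, because C5.2 relies on covariate adjustment to support missing at random.
- State which referring-service level geriatric-clinic patients take: C2.2 recruits them, and C5.1 lists three levels without one for them.
- Reconcile caregiver status between C2.3 and C5.1. If it is a stratum, add it to the model.
- Recompute Tables 4 and 5 for the stated model.

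Resource use and the retrospective-from-death analysis are outside this change.

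The cost is SAP wording and a re-run of two tables; every variable is already collected. The strata use 1 + 2 + 1 = 4 degrees of freedom. Sparse levels may need merging. If enrolment follows the eligible counts under Justification of Enrollment Estimates (assumption), BVAMC supplies 380 × 240/4920 = 18.5 patients, or 18.8 using 4860, the sum of the three listed sources (3920 + 240 + 700). That is about 3 in each of its six cells, or about 1.6 if caregiver status makes twelve.

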[figure not shown]
[figure not shown]
C APPROACH

PRELIMINARY WORK relevant to the proposed RCT.

C1.1 ENABLE Trials in cancer. We have systematically developed the evidenced-based ENABLE palliative care intervention through two large clinical trials^{49-51,63} and a recently completed, multi-site RCT (R01NR011871-01) (See figure below). The ENABLE I RWJ-funded demonstration project (1999-2001)^{49,51} provided the primary feasibility data that led to the ENABLE II efficacy RCT (NCI R01 CA101704, [name]/[name] (PI); [name]-(co-I)) published in the *Journal of the American Medical Association*⁶³, ASCO Consensus Statement,⁷⁴ Cochrane Review,¹⁴⁸ and is now under review for the NCI Research-tested Intervention Program (RTIPs). Thus, this model has become a standard of high quality cancer care.^{36,149} We have just completed the ENABLE III RCT investigating the effect of immediate vs delayed introduction of palliative care. **ENABLE III**

Preliminary Results:

demonstrated a statistically significant survival advantage at 1 year for immediate entry patients (Figure). Compared to delayed entry patients, the relative risk of death (hazard ratio [HR] (95% CI)) was lower for immediate participants at 1 year 0.72 (95% CI, 0.57-0.89) ($P=0.003$) despite small to moderate intervention effects at 12 weeks ((mean [SD]: .13 (21.39) for QOL ($P=.34$), -.21 (3.63) for symptom impact ($P=.09$), and .04 (3.91) for depressed mood ($P=.33$)).¹⁵⁰ Importantly, as shown in the Figures, there were statistically significant treatment effects of immediate entry from randomization to 12 weeks on caregiver depression: -4.1 [1.3] for depression (CESD) ($P=.003$), -1.0 [0.4] for subjective burden (SB) ($P=.02$), and a trend in QOL.¹⁵¹ **Relevance to the current study:** Provides a rigorous foundation for the intervention and methods^{36,51,63,149,152-157} to be used in the proposed trial.

C1.2 ENABLE CHF- PC: Needs assessment:

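### The decedent-only analysis is labelled an ITT analysis of the primary endpoints, and probably sits in the global test, although it keeps only patients who died

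*Combined protocol and SAP*

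**What the plan says.** All of this is in C5.2 under Specific Aim 1 unless noted.

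- **Definition of ITT.** "all randomized patients will be included in primary comparisons, regardless of whether the patient actually received the randomly-assigned intervention".
- **Label.** "We will conduct 2 sets of longitudinal ITT analyses of the primary study endpoints". One set runs forward over the 48 weeks from enrolment. The other looks at the intervention "and its effects proximal to the time to death (retrospective starting from death").
- **Conditioning.** The second set is called fully conditional "because it examines patient outcomes conditional on the patients having died", and "the participants who are alive by the end of follow-up are excluded because their outcome measures proximal to death will be unknown". The proxy-rated quality-of-dying measure (QODD) is likewise given a decedent-only analysis that is called ITT.
- **Gatekeeping.** Testing starts by "comparing all group differences simultaneously for both time periods in multiple degree of freedom global tests". Individual tests follow only if the overall result is significant.
- **Survival.** Exploratory Aim 2 notes that earlier palliative care studies altered both QOL and survival. It plans a survival comparison and a joint model.
- **Sizing (C5.3).** The plan expects 120 deaths by week 48, 60 per group. It gives detectable differences for the decedent analysis of 10.8 (KCCQ), 1.04 (MSAS-HF), 2.06 (HADS-A) and 2.01 (HADS-D). Tables 4 and 5 use a corrected two-sided 0.01 level.

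**The concern.** An analysis that removes every survivor cannot also include every randomised patient. The label matters because it decides which results may be presented as randomised evidence on the primary endpoints. Patients enter the decedent set through an event after randomisation. If the intervention changes who dies, or when, the decedents in the two arms are no longer comparable groups, and a difference between them need not be a treatment effect. Calling the analysis fully conditional names this property without removing it.

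If the set also enters the global test, that test no longer addresses only a null hypothesis protected by randomisation, and a decedent contrast could help open the gate to individual claims. The plan's own rationale (section B3) is that quality and length of life should be interpreted jointly. Yet the joint model is exploratory, while the decedent-only contrast carries the primary label.

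**Working it through.** **1. Share of patients left out.** Inputs: 380 patients, exponential survival with a 2-year (104-week) median, and independent attrition of 10% over 2 years (C5.3).

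- Table 4 check: 380 × 2^(−w/104) × 0.9^(w/104) gives 357.4, 336.1, 316.0, 297.2, 279.5 and 262.9 at weeks 8 to 48. The table shows 356, 334, 313, 294, 276 and 259, all within 3%.
- On the stated 120 deaths: 260/380 = 68.4% are left out.
- On the stated survival assumption: deaths by week 48 = 380 × (1 − 2^(−48/104)) = 380 × (1 − 0.726) = 104.0, so 72.6% are left out. Counting only deaths that precede attrition gives 101.7, or 73.2%.
- The paragraph also requires at least one follow-up assessment. With λ = ln 2/104 and μ = −ln 0.9/104, deaths among patients still followed at week 8 are 380 × λ/(λ+μ) × [e^(−8(λ+μ)) − e^(−48(λ+μ))] = 82.0, so 78.4% are left out.

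The 120 does not follow from a 2-year median. It is approached by 380 − 259 = 121, which counts attrition as death, or by 380 × (1 − 0.68) = 121.6, using the 1-year survival given for the log-rank calculation. A 2-year median implies 2^(−0.5) = 0.707 at one year, not 0.68.

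**2. Significance level.** A two-sample t calculation (noncentral t, power 0.80, SDs 21, 2.01, 4.0 and 3.9 from Table 4) gives these detectable differences:

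| n per group | alpha | KCCQ | MSAS-HF | HADS-A | HADS-D |
|---|---|---|---|---|---|
| 60 | 0.05 | 10.83 | 1.04 | 2.06 | 2.01 |
| 60 | 0.01 | 13.29 | 1.27 | 2.53 | 2.47 |
| 52 | 0.05 | 11.65 | 1.11 | 2.22 | 2.16 |

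The stated values match the first row only. At 0.01 with 60 per group, power for 10.8 KCCQ points is about 0.60 (normal approximation). The analysis is therefore primary by label but sized outside the corrected level.

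**3. Place in the global test.** The only two periods named in that paragraph are forward from baseline and backward from death. That makes the from-death set the natural second period. The phrase is never defined, however, and the sentence comes before the second analysis is described.

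**4. Size of selection bias.** No figure in the documents fixes this, so the following is illustrative. Assume no true QOL effect, an intra-subject correlation of 0.5, control survival as in the plan, and mortality rising 1.5- to 2.0-fold per SD of worse QOL (an assumption; the documents give no such link). Take a survival HR of 0.72 from the earlier cancer trial (C1.1: "at 1 year 0.72 (95% CI, 0.57-0.89")), or 0.625 (= 1/1.6, the HR the plan says it can detect). With HR 0.72, deaths by week 48 are 190 × (1 − 0.726) = 52 against 190 × (1 − 0.726^0.72) = 39. Simulated decedent contrasts shift by about 0.02 to 0.06 SD at HR 0.72 and up to about 0.08 SD at HR 0.625. That is 0.02 × 21 = 0.4 to 0.08 × 21 = 1.7 KCCQ points, against a stated detectable difference of 10.8. Other simulated versions gave less than 1 point.

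**The case against.** The plan hides nothing: it states the conditioning, the exclusion and the reason for it. The term ITT may be used loosely to mean analysed as assigned, as its use for the QODD suggests. C5.3 gives the decedent detectable differences after, and apart from, the statement about the primary aims, and they match an uncorrected 0.05. That suggests the authors did not place this analysis in the corrected family. The plan says the intervention is not directly intended to affect survival, and it projects equal deaths in the arms. The HR of 0.72 comes from a cancer trial of immediate against delayed entry.

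Much of this stands. A reader might infer that a positive primary result could arise from selection alone. The documents do not support that: the simulated shifts are small, and under the assumed link they run against the intervention, because the treated patients who still die are the sicker ones. A shift as large as 0.42 SD would need all 13 averted deaths (52 − 39) to come from one tail of QOL, which is an extreme bound. Nor do the documents establish that the decedent set is in the global test.

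The forward analysis is not free of the problem either. The plan calls it partially conditional on being alive, and it needs at least one follow-up assessment. It does start from both randomised arms, whereas the decedent set is defined entirely by the later event. Disclosure and loose usage do not make a decedent-only analysis meet the written definition.

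**Conclusion.** The contradiction holds on the text alone: an analysis restricted to decedents is presented as ITT on the primary endpoints, against the plan's own definition. It leaves out 68% of patients on the stated 120 deaths and about 73% on the stated survival assumption, or about 78% if a week-8 assessment is needed. The 73% is derived, not a figure in the plan. The contrast is not protected by randomisation if treatment affects mortality, which Exploratory Aim 2 treats as worth testing.

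Its entry into the gatekeeping test is the most natural reading but unconfirmed. Its significance level is inconsistent with the primary label. The expected bias is small under assumptions that the documents do not supply, so the finding concerns estimand, label and gatekeeping, not a demonstrated distortion. It should be corrected before analysis.

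**What to change.** 1. Reserve primary status and the global test for the forward analysis, and state that it is partially conditional on being alive.
2. Define the two time periods in the global test accordingly.
3. Relabel the from-death analysis and the QODD analysis as secondary, conditional on death, analysed as assigned, not ITT.
4. Base death-adjusted treatment claims on the survival-weighted cumulative QOL comparison from the joint model in Exploratory Aim 2. The backward-from-death contrasts in that model are themselves fully conditional and do not serve this purpose.
5. State the alpha for the decedent analysis, reconcile the 120 deaths with the 2-year median (or correct the assumption), and restate the detectable differences to match.

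The cost is SAP wording and a short recalculation. No data or analyses are lost; the downside is that one fewer analysis carries primary status.
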